3.0 METHODS

3.1 Study Design

A multi-center prospective cohort study, with a pre- versus post-comparison, evaluating how making PREDICT 2.1 results available to treating physicians impacts on subsequent ordering of Oncotype DX ®, chemotherapy use, time to commencement of chemotherapy, and health care resource utilization. In addition, in order to understand physician reasoning and comfort with making systemic therapy decisions with either PREDICT 2.1, Oncotype DX ® or both, a physician questionnaire will be performed in order to drive subsequent knowledge mobilisation strategies.

The study will involve participation from 6-8 Ontario sites that will be chosen to reflect a diverse patient population in Ontario and the site's involvement in the REaCT program.

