3.7 Study Outcomes

Primary Endpoint: The primary outcome will be the proportion of patients for which Oncotype DX ® is ordered, defined as the number of patients with Oncotype DX ® orders divided by the number of patients eligible for Oncotype DX ® testing.

Secondary Endpoints:

Frequency and type of chemotherapy used will be collected from the patient's electronic medical record as will timing to start chemotherapy, radiation therapy and endocrine therapy. Prognostic risk scores, including Magee formulae, Gage and Tennessee equations will be calculated using patient and tumour characteristics. These scores will also be compared with Oncotype DX ® results when performed. Physician questionnaire results will be used to assess physician comfort when making systemic therapy decisions.

Economic analysis:

We will conduct a cost analysis and compare total health system costs before and after the model implementation from the Ontario government's perspective.

The cost components will include Oncotype DX cost (C\$4380), adjuvant chemotherapy cost and other health services costs. We assume that the PREDICT 2.1 tool is readily available at no cost. The cost associated with other health services among patients who receive and those who do not receive adjuvant chemotherapy (including cost of cancer clinic, in-patient services, physician billing, chemotherapy, endocrine therapy, supportive drug, home care, in-patient and emergency department costs) [26] will be obtained from a concurrent cohort study and Canadian sources. Based on this analysis, we will then extrapolate the cost findings to the entire population of Ontario to report the financial implications of our intervention to Cancer Care Ontario.

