3.8 Data Collection

Data collection begins when a pathology report is completed and deemed eligible for Oncotype testing under the Ontario criteria. The following information will be collected from the patient's electronic medical record:

- Eligibility for Oncotype DX ® (ODX) reimbursement by OHIP (histologically confirmed primary breast cancer, no prior chemotherapy, ER positive, PR positive or negative, HER2 negative, lymph node status negative or micro-invasive disease, tumour >1 cm in size (or if ≤1cm, must be grade 2/3 or have lymph node micrometastasis))

- Whether ODX was ordered and if so, the ODX recurrence score
- Data required for PREDICT 2.1 algorithm (age, menopause, ER/Her2/Ki67 status, tumor size, tumor grade, method of detection, number of positive lymph nodes)
- Which chemotherapy regimen was planned and what chemotherapy the patient received
- Time from medical oncologist visit to starting chemotherapy

Data collected will be de-identified (no patient identifiers) and will not be linked to the treating physician. Data will be entered by the CRA at each site into a secure study-specific database.

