4.0 STATISTICAL ANALYSIS

The primary analysis will be based on a hierarchical logistic regression analysis, with time period (pre-intervention versus post-intervention) as the primary covariate of interest. For this model, patient characteristics are considered nested within treating physician, which is nested within treatment centre. Adjustments will be performed for baseline characteristics. From our survey, it was evident that there was significant variability between centres (and between physicians) for ordering Oncotype DX. Data from Ottawa shows that approximately 15% of approximately 600 patients treated by 8 physicians have this test performed. In contrast, Kingston (5 physicians) sees around 200 eligible patients a year and Oncotype DX is ordered for around 65% of these patients,

Thunder Bay (3 physicians) sees around 70 patients a year and also tests around 65% of eligible patients, and Newmarket (3 physicians) sees around 130 eligible patients a year and Oncotype DX is ordered for around 75% of these patients. Windsor (3 physicians) and Kitchener (4 physicians) both see around 150 patients per year and orders Oncotype DX testing on 90% of eligible patients. Given concerns that use of hierarchical clusters may not sufficiently account for the substantial variability between sites, analyses will also be conducted by site, grouped by baseline rate of testing (i.e. Kingston, Thunder Bay and Newmarket will be combined, as will Windsor and Kitchener; Ottawa will be a separate group on its own). A similar analysis will be performed using hierarchical logistic regression. In addition, key supportive analyses will also be performed using a two-sample chi-square test within each site separately, comparing the change in proportion of patients for which Oncotype DX is ordered for each physician (i.e. post-intervention proportion – pre-intervention proportion for physician A, B, C, ...).

Analyses of secondary endpoints will be performed globally across all sites combined, and for each site individually. The chi-square test or Wilcoxon rank sum test will be used as appropriate for categorical or continuous endpoints respectively. Results will be presented using tables and figures, and exact confidence intervals will be constructed for outcomes of interest. Bootstrapping may be used for estimation purposes if required. All tests will be two-sided and statistical significance will be defined at the $\alpha=0.05$ level.

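### Chemotherapy use, type and timing are compared before and after PREDICT 2.1 without adjustment for patient case mix, although the main test-ordering models are adjusted

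*Combined protocol and SAP*

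**What the plan says.** Section 3.1 describes "A multi-center prospective cohort study, with a pre- versus post-comparison". Patients are not randomised, and the two periods contain different patients.

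For Oncotype DX ordering, Section 4.0 states: "The primary analysis will be based on a hierarchical logistic regression analysis, with time period (pre-intervention versus post-intervention) as the primary covariate of interest". It adds: "Adjustments will be performed for baseline characteristics". No covariate is named. A similar hierarchical model is planned by site group. The supportive within-site chi-square tests of ordering are unadjusted.

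For the secondary endpoints the same section states "Analyses of secondary endpoints will be performed globally across all sites combined, and for each site individually", and then: "The chi-square test or Wilcoxon rank sum test will be used as appropriate for categorical or continuous endpoints respectively". It plans no regression, patient-level stratification, weighting or standardisation for them. The significance level is two-sided 0.05.

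Section 3.7 gives the endpoints affected: "Frequency and type of chemotherapy used will be collected from the patient's electronic medical record as will timing to start chemotherapy, radiation therapy and endocrine" (the last item being endocrine treatment). Section 3.8 lists the data collected to run PREDICT: "age, menopause, ER/Her2/Ki67 status, tumor size, tumor grade, method of detection, number of positive lymph nodes".

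**The concern.** Whether a patient receives chemotherapy depends on who the patient is. The Introduction says so itself. It reports that chemotherapy benefit is larger for a 5.0 cm than for a 0.6 cm tumour, smaller at lower clinical risk, and different either side of age 50 at recurrence scores of 21-25. If the post-intervention patients differ from the pre-intervention patients in age, grade or size, the chemotherapy rate will move even if PREDICT 2.1 changes no decision. A chi-square or rank-sum comparison of the periods attributes that movement to the intervention. Analysing each site alone removes differences in site mix but not in patient mix.

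Chemotherapy frequency, type and timing are stated secondary objectives (Section 3.6). Adjuvant chemotherapy cost, and other health-service costs by chemotherapy receipt, enter the before/after cost comparison, which is then extrapolated to Ontario (Section 3.7). A case-mix artefact could therefore reach a provincial cost estimate.

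**Working it through.** **The plan's own figures.** Section 5.0 gives power for Oncotype DX ordering only. Those figures reproduce. The continuity-corrected numbers per period for 80% power are 301, 150 and 185, against 300, 150 and 185 in the plan. An odds ratio of 0.67 from 50% with 500 per period has 88.2% power, consistent with the stated figure of over 80%. There is no stated figure for a secondary endpoint to reproduce.

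**Inputs.**
- Patients per period: 500 (the plan's conservative total) to 300 + 75 + 75 + 75 + 35 + 75 = 635 (sum of the six centres). Both are from Section 5.0.
- Assumed, not in the documents: grade 3 share 20% before the intervention; chemotherapy use 60% in grade 3 and 15% otherwise; no true period effect within grade.

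**Formulae.** With s the grade 3 share, the crude rate is p = 0.60s + 0.15(1 − s). The standard error of the difference is SE = √[(p₀(1 − p₀) + p₁(1 − p₁))/n]. The rejection probability is about P(|Z + (p₁ − p₀)/SE| > 1.96).

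**Results.** p₀ = 0.20 × 0.60 + 0.80 × 0.15 = 0.240.

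| Shift in grade 3 share | p₁ | SE (n = 500; 635) | (p₁ − p₀)/SE | Rejection |
|---|---|---|---|---|
| none | 0.2400 | 0.0270; 0.0240 | 0 | 5% |
| 2 points | 0.2490 | 0.0272; 0.0241 | 0.331; 0.373 | 6.3%; 6.6% |
| 5 points | 0.2625 | 0.0274; 0.0243 | 0.821; 0.925 | 13.0%; 15.2% |
| 10 points | 0.2850 | 0.0278; 0.0247 | 1.62; 1.82 | 36.6%; 44.5% |

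The bias itself is the shift times the difference in rates. For 5 points it is 0.05 × (0.60 − 0.15) = 0.0225, or about 0.0225 × 635 = 14 patients.

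**Milder assumption.** The same formulae with 50% and 20% chemotherapy use give 8-9% rejection for a 5-point shift and 19-22% for 10 points.

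**Does adjustment cure it?** A simulation used 500 per period, 4,000 runs, a 25% initial high-risk share, and high/low-risk chemotherapy rates of 50%/20%, 60%/15% or 70%/10%. The unadjusted chi-square test rejected in 8-19% of runs for a 5-point shift and 18-56% for 10 points. A Cochran-Mantel-Haenszel test stratified by risk group, a simple stand-in for regression adjustment, stayed between 4.5% and 5.8% throughout.

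**Precision.** Take the 60%/15% setting with no shift, 635 per period and a conditional odds ratio of 0.67. The post-period rates become 0.67 × 1.5/(1 + 0.67 × 1.5) = 0.501 in grade 3 and, likewise, 0.106 otherwise, so the crude rate is 0.185. The log odds ratio is −0.331 (SE 0.138) crude and −0.400 (SE 0.152) adjusted. The ratios are 2.40 and 2.63: the test gains power although the adjusted standard error is larger.

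**The case against.** The strongest reply is that no shift is shown. The eligibility criteria are the same in both periods, at the same sites, in consecutive six-month windows, and nothing in the documents says referral changes. Chance imbalance is already covered by the 5% error rate; only a systematic shift inflates it. A 5-point shift at 635 per period is about 2.1 standard errors (0.05/0.0234), more than chance usually produces. All this stands, and it makes the concern conditional. It does not remove it: the criteria admit a wide range of ages, sizes and grades, and Section 6.0 places the two periods in different parts of the year.

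Three stronger inferences are tempting and not supported:
- A reader might infer that the planned tests are biased as they stand. They are biased only if case mix changes systematically.
- A reader might infer that the ordering model already adjusts for age, grade and size, so that its covariates can simply be reused. The plan names none.
- A reader might infer a sizeable saving in patients from adjustment. With variance explained R² = 0.20 × 0.80 × 0.45²/(0.24 × 0.76) = 0.178, the gain 1/(1 − R²) − 1 is about 20%. It falls to about 8% with rates of 50%/20% and 4% with 40%/20%, and it is a gain in test power only.

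It is also fair to object that the ordering model cannot be copied unchanged. It nests patients within physician, whereas Section 3.8 says the data will not be linked to the treating physician. The fix must therefore work at centre level.

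The caution that Section 4.0 promises for secondary endpoints concerns multiple testing, so it does not answer a confounding point.

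**Conclusion.** The concern holds as a gap in the analysis plan; no stated figure is wrong. The plan adjusts its main models for test ordering and leaves chemotherapy outcomes unadjusted in a non-randomised comparison, although it collects the relevant variables. If case mix is stable, the planned tests keep their 5% level. If it shifts, the false-positive rate under the stated assumptions is about 6-7% for 2 points, 13-15% for 5 and 37-45% for 10. Those sizes depend on an assumed grade 3 share and assumed chemotherapy rates, and are smaller when the rates differ less by grade. Because the endpoints are secondary and the bias is conditional, this is a change that should be made; it does not undermine the primary analysis.

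**What to change.** Make the main analysis of chemotherapy use a logistic regression on period with centre effects and covariates named in advance from those already collected: age, tumour size, grade and nodal status. Add a physician level only if that link is recorded. Use matching adjusted regressions for the other endpoints, for example multinomial for chemotherapy type (with none as a category) and a time-to-event model for timing. Keep the chi-square and Wilcoxon results as unadjusted descriptive comparisons. Report a standardised risk difference beside the odds ratio, because the adjusted odds ratio is conditional rather than marginal.

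The cost is SAP wording and a few extra models. Patients with missing covariates may drop out, since the plan excludes imputation except where the value is obvious; their number should be reported. Small sites, such as Thunder Bay with about 35 patients per period, need fewer covariates or descriptive reporting only. Adjustment does not remove calendar-time trends, and the report should say so.

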3.6 Study Objectives

Primary Objective:

To assess whether providing individual patient prognostic and predictive scores from PREDICT 2.1 affects the rate of subsequent requests for Oncotype DX testing.

Secondary Objectives:

To assess whether routine availability of PREDICT 2.1 affects: the frequency of chemotherapy use, type of chemotherapy use, the time to starting chemotherapy, endocrine therapy or radiation therapy and Oncotype DX ® cost and total health system costs and subsequent health care utilization. In order to use these study findings for knowledge mobilisation strategies, we need to understand physician's reasoning and comfort with making systemic therapy decisions.

Physicians will therefore complete a questionnaire [25] after seeing each patient.

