5.0 SAMPLE SIZE

Sample size calculations for hierarchical regression models are difficult, as they require estimates of the number of clusters, the size of each cluster, the effect of intervention on each cluster separately and intra-cluster correlation. Without prior information, these estimates are unlikely to be accurate. Hence, statistical power and sample size calculations will be based on practical considerations.

It is hypothesized that if the use of PREDICT 2.1 decreases the odds of Oncotype DX ordering by approximately 50% or more, the usage of Predict 2.1 will be of clinical importance. It is known that approximately 300 patients are seen in a given six-month period in Ottawa, and approximately 15% of eligible patients undergo Oncotype DX testing. For the other centres, the values are 75 and 75% (Newmarket), 75 and 90% (Windsor), 75 and 65% (Kingston), 35 and 65% (Thunder Bay), and 75 and 90% (Grand River). Based on these estimates,

a simple, two-sided, $\alpha=0.05$, logistic regression model would have 80% power to detect an odds ratio of 0.46 (from 15% to 7.46%) in Ottawa, an odds ratio of 0.38 (from 90% to 77.4%) in Grand River/Windsor, and an odds ratio of 0.53 (from 70% to 55.4%) in Newmarket/Kingston/Thunder Bay. Overall, if one conservatively estimates at least 500 patients will be eligible pre-intervention and 500 patients will be eligible post-intervention, a simple logistic regression analysis would have over 80% power (2-sided, $\alpha=0.05$) to detect an odds ratio of 0.67, assuming that approximately 50% of patients undergo Oncotype DX testing in the pre-intervention period. Combined, these estimates give assurance that the sample size for this study is sufficient to capture clinically meaningful effects.

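### The all-site tests of secondary endpoints ignore centre; stratifying by centre is a nearly free improvement of modest priority

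*Combined protocol and SAP*

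**What the plan says.** Section 4.0 gives the primary endpoint, Oncotype DX ordering, a hierarchical logistic model with patients nested in physicians and physicians in centres. Because of a worry that this "may not sufficiently account for the substantial variability between sites", it adds analyses grouped by baseline testing rate and tests within each site.

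Secondary endpoints are treated more simply. "Analyses of secondary endpoints will be performed globally across all sites combined, and for each site individually". The tests are then named: "The chi-square test or Wilcoxon rank sum test will be used as appropriate for categorical or continuous endpoints respectively". No stratification, centre term or model is given for the all-site version, and no other section supplies one.

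The secondary objectives in section 3.6 cover chemotherapy use and type, times to treatment, and "Oncotype DX ® cost and total health system costs". Section 3.7 compares costs before and after implementation and extends the result to Ontario, but names no estimator for the cost difference.

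On timing, sections 3.3 and 3.4 give each site its own start date, with teaching six months after activation. Section 6.0 gives a single calendar: sites initiated December 2019 to February 2020, first six months complete in May 2020, teaching in June, second six months complete in December 2020.

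**The concern.** The plan treats differences between centres as a main threat to the primary analysis, then drops centre from the combined secondary tests. Three situations need to be kept apart.

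- If centres do not differ on an endpoint, ignoring centre does no harm.
- If they differ and each centre contributes the same share before and after, false positives are not inflated. The test does count between-centre spread as noise, and power can fall.
- If they differ and the shares change, the pooled comparison mixes the change in shares with any change in practice.

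At stake are modest amounts of power for chemotherapy use, possibly more for treatment times, and the integrity of a cost difference that is meant to inform provincial spending.

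**Working it through.** **1. The plan's own figures.** Section 5.0 gives power for ordering only; no power is stated for any secondary endpoint. Its figures reproduce. For 80% power, the two-proportion formula with continuity correction needs 301, 150 and 185 patients per period for the three site groups, against 300, 150 and 185 planned. Overall, an odds ratio (OR) of 0.67 from 50% gives 0.67/1.67 = 40.1%, and 500 per period gives 88.2% power, consistent with the stated figure of over 80%.

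**2. Inputs.** Six-month volumes and ordering rates from section 5.0: Ottawa 300 (15%), Newmarket 75 (75%), Windsor 75 (90%), Kingston 75 (65%), Thunder Bay 35 (65%), Grand River 75 (90%). The total is 635. Expected orders are 45 + 56.25 + 67.5 + 48.75 + 22.75 + 67.5 = 307.75, or 48.46%. Section 4.0 implies 100 for Kingston ("Kingston (5 physicians) sees around 200 eligible patients a year") and 65 for Newmarket ("Newmarket (3 physicians) sees around 130 eligible patients a year"). The total then becomes 650 and the rate 48.7%, which changes little.

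**3. Why pooling can lose power.** The pooled chi-square test uses p̄(1−p̄), where p̄ is the overall rate. The stratified test uses the average of p(1−p) within centres. As an example, assume chemotherapy rates of 10–50%, rising linearly with ordering: 10% + 40% × (ordering rate − 15%)/75%. The centre rates, in the order above, are 10, 42, 50, 36.7, 36.7 and 50%, and p̄ = 176.83/635 = 27.8%. The pooled variance term is 0.278 × 0.722 = 0.201. The within-centre average is 108.3/635 = 0.171, about 15% smaller.

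**4. Chemotherapy use.** Simulated power with a common within-centre OR of 0.67, pooled chi-square against Cochran-Mantel-Haenszel (CMH). All centre rates are assumptions, tried in both directions relative to ordering, with fixed and Poisson volumes.

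| Centre rates | Pooled | CMH | Lost by pooling |
|---|---|---|---|
| All 25% | 83.3% | 83.2% | none |
| 15–35% | 79.5 to 82.3% | 80.6 to 83.7% | about 1 point |
| 10–50% | 75.2 to 81.9% | 81.2 to 85.1% | 3–6 points |

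A 20–25% range also loses about nothing. At OR 0.50 pooled power is at least 99.4% throughout, and the loss is 0.4 point or less.

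**5. Treatment times.** Assumed: 160 treated patients per period (75, 19, 19, 19, 9, 19), normal errors, shift 0.3 SD.

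| Between-centre SD (within-centre SD = 1) | Wilcoxon | Van Elteren |
|---|---|---|
| 0 | 74.2% | 73.5% |
| 0.25 | 73.2% | 73.9% |
| 0.5 | 67.2% | 73.2% |
| 1.0 | 46.4% | 73.3% |

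The last Wilcoxon figure ranges over 46–53% with how centre effects are set; the loss is 20 points or more either way. With no true effect and a stable mix, Wilcoxon rejects in 5.1, 4.4, 2.6 and 1.0% of runs. It becomes conservative, not liberal.

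**6. Mix shift and Oncotype cost.** Suppose no centre changes its ordering. The apparent change is 48.46% minus Σ(volume × months/6 × rate)/Σ(volume × months/6). Multiplying by C$4380 gives the cost per eligible patient. Each of six sites may start in December, January or February: 3⁶ = 729 combinations, equally weighted, with a full post period.

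- *Pre period stops at the end of May (6, 5 or 4 months).* The median absolute shift is 2.37 points, or 0.0237 × 4380 = C$104. The extreme has Ottawa at 6 months and the others at 4: 220.17/523.33 = 42.07%, a shift of 6.39 points or C$280.
- *Pre period runs to late June, capped at six months (6, 6 or 5).* The median is 1.19 points, or C$52. The extreme has Ottawa at 6 months and the others at 5: 263.96/579.17 = 45.58%, a shift of 2.89 points or C$127.

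**7. Mix shift and chemotherapy tests.** On the May reading, the median false-positive rate is 5.0%, 5.2–5.7% and 5.8–7.7% for assumed ranges of 20–25%, 15–35% and 10–50%. In the widest range it exceeds 10% in 20–32% of combinations. On the June reading, no combination exceeds 10% even at 10–50%.

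**The case against.** The strongest reply is that harm to any planned secondary test rests on centre differences that the documents do not report. That stands: with moderate differences the loss is about a point, and the larger figures need wide assumed spreads.

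A reader might infer a large power deficit by applying the 15–90% ordering rates to a pooled chi-square test. The documents do not support this. Ordering is the primary endpoint and has its own hierarchical model; no planned secondary test uses a pooled chi-square on it. The ordering rates matter here only through Oncotype cost, where no test is named and the issue is bias in a difference.

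A reader might also infer that the mix will shift and that an artefact will be projected onto Ontario. That goes too far. Site-specific six-month periods, as sections 3.3 and 3.4 describe, would keep the mix close to balanced. The scenarios arise only if section 6.0 is taken literally or volumes change unequally, and the choice between May and June halves the median. Since section 3.7 gives no cost estimator, the artefact could be carried forward; it is not shown that it would be.

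The site-by-site tables would help to expose a shift, and section 4.0 promises caution with secondary endpoints. Both mitigate, but neither gives a combined, centre-adjusted result.

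**Conclusion.** The point holds as a low-cost improvement of modest priority. The all-site secondary tests ignore centre, and nothing else in the plan adjusts them. For chemotherapy use, the loss at OR 0.67 runs from nothing to 3–6 points over the assumed ranges, and is almost nil at OR 0.50. For treatment times it is about 1, 5–6 and 20 or more points at between-centre SDs of 0.25, 0.5 and 1.0. The true position within these ranges is unknown. For Oncotype cost, the scenario medians of about 1.2–2.4 points (C$52–104 per eligible patient) are illustrations, not expected values. Section 6.0 cannot give a site opened in February six months before teaching in June, so it conflicts with sections 3.3 and 3.4 and they must be reconciled. The comparison of risk scores with Oncotype results is not a pre-post comparison and is unaffected.

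**What to change.** In section 4.0, make the all-site secondary comparisons centre-stratified:

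- Categorical endpoints: Cochran-Mantel-Haenszel test (generalised form for type of chemotherapy) or logistic regression adjusted for centre.
- Continuous endpoints: van Elteren test or a centre-adjusted model.
- Report centre-adjusted confidence intervals for the combined pre-post differences.
- Compute Oncotype and total cost differences within centre, then combine them, before extending to Ontario.
- Keep the simple tests for the by-site tables.

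Reconcile the section 6.0 calendar with sections 3.3 and 3.4. As a minor tidy-up, align the Kingston and Newmarket volumes in sections 4.0 and 5.0.

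The cost is SAP wording and a little programming. Data are entered by site, so no new data or patients are needed. When centres are alike, the power cost is 0–0.2 point for CMH and 74.2 − 73.5 = 0.7 point for van Elteren. Physician terms are not part of this change, because section 3.8 says the data are not linked to the treating physician. State that stratifying does not remove time drift or physician clustering, and does not make a sample that is 300/635 = 47% Ottawa representative of the province.
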